12.6. Questionnaires and scales completed by the subject

12.6.1. FARS -Activities of Daily Living (FARS-ADL)

The subject self-administered FARS-ADL is a sub-scale of the FARS. There are nine questions regarding activities of daily living. The ADL is scored from 0 to 36, with higher score representing more severe progression. The FARS-ADL will be collected at Screening, on Day 1, Day 120 (± 30 days), Day 240 (± 30 days), and Day 330 (± 30 days). Refer to Section 19.4 for the specific items assessed.

12.6.2. SF-36

The SF-36 is a well validated 36-item subject self-administered Short Form Health Survey and is a set of generic, coherent and easily administered quality-of-life measures. The SF-36 will be collected at Screening, on Day 1, Day 120 (\pm 30 days), Day 240 (\pm 30 days), and Day 330 (\pm 30 days). Refer to Section 19.5 for the specific items assessed.

12.6.3. Patient Global Impression of Change (PGI-C) Scale

The Patient Global Impression of Change (PGI-C) Scale is a qualitative assessment of change completed by the subject using a 7-item scale ranging from "very much worse" to "very much improved". The PGI-C will be collected at Day 120 (\pm 30 days), Day 240 (\pm 30 days), and Day 330 (\pm 30 days). In between the clinic visits the subject will be contacted by phone by a study site staff member and asked to complete the PGI-C. This will be done after 30, 60, 90, 150,

180, 210, 270 and 300 days of dosing. All calls have a window of \pm 7 days. Refer to Section 19.6 for the specific items assessed.

12.6.4. Visual Analogue Scale (VAS)

The subject will complete a VAS for Improvement of FA Symptoms and a VAS for fatigue. The VAS for Fatigue will be completed at Screening, on Day 1, Day 120 (\pm 30 days), Day 240 (\pm 30 days), and Day 330 (\pm 30 days). VAS for Improvement of FA Symptoms will be completed on Day 120 (\pm 30 days), Day 240 (\pm 30 days), and Day 330 (\pm 30 days). Refer to Section 19.7 for the VAS.

12.6.5. Fatigue Scale

The subject will complete a Fatigue scale at Screening, on Day 1, Day 120 (\pm 30 days), Day 240 (\pm 30 days), and Day 330 (\pm 30 days). In between the clinic visits the subject will be contacted by phone by a study site staff member and asked to complete the Fatigue scale. This will be done after 30, 60, 90, 150, 180, 210, 270 and 300 days of dosing. All calls have a window of \pm 7 days. Refer to Section 19.8 for the specific items assessed.

12.6.6. Neuro-QoL scales

The subject will complete the Neuro-QoL scale for upper extremity function and lower extremity function. These scales will be collected at Screening, on Day 1, Day 120 (\pm 30 days), Day 240 (\pm 30 days), and Day 330 (\pm 30 days). In between the clinic visits the subject will be contacted by phone by a study site staff member and asked to complete the Neuro-QoL scales. This will be done after 30, 60, 90, 150, 180, 210, 270 and 300 days of dosing. All calls have a window of \pm 7 days. Refer to Section 19.9 for the specific items assessed.

12.6.7. Fall Questionnaire

The subject will complete a Fall questionnaire at Screening, on Day 1, Day 120 (\pm 30 days), Day 240 (\pm 30 days), and Day 330 (\pm 30 days). In between the clinic visits the subject will be contacted by phone by a study site staff member and asked to complete questions 8 and 9 of the fall questionnaire. This will be done after 30, 60, 90, 150, 180, 210, 270 and 300 days of dosing. All calls have a window of \pm 7 days. Refer to Section 19.10 for the specific items assessed.

12.6.8. Fall Diary

The subjects will be asked to keep a daily log (diary) documenting falls, near-falls, stumbles, and fear of falling from screening until the end of treatment. Falls are defined as any event that results in unintentionally falling to the ground. Near-falls are defined as losing balance with no fall to the ground (e.g. hold on to something/somebody, or fall onto a chair, bed, or other soft landing). Stumbles are defined as losing balance momentarily with regaining of footing and no fall.

12.6.9. Speech Assessment Questionnaire

The subject will complete a Speech Assessment Questionnaire to evaluate his/ her speech pattern and communication style at Screening, on Day 1, Day 240 (± 30 days), and Day 330 (± 30 days). Parent/caregiver/travel companion will also have to complete one question on this questionnaire. Refer to Section 19.11 for the specific items assessed.

12.7. Safety

Safety assessments include AEs, physical and neurologic examinations, vital signs, 12-lead electrocardiogram (ECG), and clinical laboratory tests (hematology, clinical chemistry, lipid profile, coagulation, and urinalysis). Safety signals must be promptly communicated to the Medical Monitor.

12.7.1. Adverse Events

Subjects will be assessed for AEs at each study visit after the informed consent is obtained through the end of the study. Adverse events will be evaluated for incidence, severity, and relationship to study drug. The safety evaluation will include an assessment of all AEs, SAEs, and dose discontinuations due to adverse event. Monitoring and grading of AEs will be done in accordance with Medical Dictionary for Regulatory Activity (MedDRA) during the study. See Section 15 for additional information.

12.7.2. Physical Examination

Complete physical examinations will be conducted at Screening, Day 1, Day 120 (± 30 days), Day 240 (± 30 days), and Day 330 (± 30 days). Physical examinations include skin, HEENT, respiratory, cardiovascular, gastrointestinal, endocrine/metabolic, neurological, blood/lymphatic, musculoskeletal, hepatic, allergies and psychological/psychiatric examinations.

12.7.3. Vital Signs

Vital signs (systolic and diastolic blood pressure, heart rate, respiration rate, temperature) and weight will be measured at each site visit. All measurements should be performed in the supine/semi-supine or seated position after the subject has rested in that position for at least 3 minutes. Blood pressure will be obtained with an automated or manual blood pressure apparatus in the same position. Blood pressure and pulse should be performed on the same extremity throughout the study and documented as such. Height and BMI will be measured at Screening and at Day 330.

12.7.4. 12-Lead Electrocardiogram

A single ECG reading will be obtained at each site visit [Screening, Day 1, Day 120 (\pm 30 days), Day 240 (\pm 30 days), and Day 330 (\pm 30 days)]. If the Screening and Day 1 visit are within

7 days (or less) of each other, the ECG does not have to be repeated, unless to rule out any clinically significant findings. A copy of the tracing should be retained as a source document. The Investigator will review each ECG and provide an interpretation of the ECG as to whether the ECG is: (1) within normal limits compared with Baseline and within normal limits for a FRDA population, (2) or abnormal with any clinically significant findings noted. Clinically significant changes will be recorded as AEs.

Individuals with FRDA show substantial variance in ECG readings; typical ECG changes in subjects with FRDA may be assessed as clinically significant in other populations. Underlying disease must be considered when evaluating ECG changes.

12.7.5. Clinical Laboratory Tests

The following clinical laboratory tests will be performed at each site visit [Screening, Day 1, Day 120 (\pm 30 days), Day 240 (\pm 30 days), and Day 330 (\pm 30 days)] at a local approved laboratory. If the Screening and Day 1 visit are within 7 days (or less) of each other, the laboratory tests do not have to be repeated, unless to rule out any clinically significant findings. The safety laboratory tests, and lipid profile should be performed in a fasting state:

- Hematology: hematocrit, hemoglobin, mean corpuscular hemoglobin, mean corpuscular volume, mean platelet volume, platelet count, red blood cell (RBC) count, and white blood cell (WBC) count with differential (absolute).
- Coagulation: prothrombin time (PT), international normalized ratio (INR), and partial thromboplastin time (PTT).
- Clinical chemistry: ALT, AST, alkaline phosphatase, total bilirubin, amylase, lipase, calcium, magnesium, glucose, sodium, potassium, carbon dioxide (CO₂), chloride, blood urea nitrogen (BUN), and creatinine.
- Urinalysis (only at screening and Day 330): dipstick test and a microscopic examination if clinically indicated.
- Lipid profile: total cholesterol, high density lipoprotein (HDL), low density lipoprotein (LDL) and triglycerides.

Women will be tested for pregnancy by serum pregnancy test at Screening and by a urine pregnancy test at subsequent visits (including EOT), unless there is documented evidence confirming they are not of childbearing potential. Subjects should be counseled to avoid pregnancy for at least 30 days after all study procedures are completed (see Section 9.4). A Urine Pregnancy test is to be performed by the subject at home on the day of the EOT phone call (before the call and after the last dose). Subjects taking the Urine Pregnancy Test will telephonically confirm the result with the site, scan and email/fax a photo of the result to the site.

12.7.6. Columbia-Suicide Severity Rating Scale

This scale will be administered at Screening to identify if the subject has suicidal ideation or suicidal behavior.

12.7.7. Echocardiogram

Subjects will need to get an echocardiogram done at Screening if there has not been an echocardiogram obtained in the 12 months prior to screening. An echocardiogram obtained up to 12 months prior to Screening can be used for the assessment of the eligibility in the study. A repeat echocardiogram will be obtained on Day 330 (± 30 days).

12.8. Pharmacokinetics

12.8.1. Sample Collection

Bioanalytical measurements will be performed to determine the concentration of D2-LA, D2-ARA, H2-LA and H2-ARA in plasma and red blood cells. Blood samples will be collected for plasma measurements and assessment in red blood cells at month 4 (Day 120 ± 30 days), at month 8 (Day 240 ± 30 days), and month 11 (Day 330 ± 30 days). Samples are to be obtained prior to dosing and prior to breakfast. Actual collection time points should be recorded and will be used for PK analysis. Best efforts to collect the samples at the planned time should be made.

Protocol-specific instructions will be provided to each site in a Study Lab Manual for the collection, handling, storage, and shipping of PK (plasma and RBC) samples. The date and actual time each sample is collected will be recorded. Date and time of last dose prior to sample collection will also be recorded.

Two additional optional PK sub-studies will be offered. The first is a 24hr PK Profile at steady state that will occur immediately before or after the Day 330 visit. At the time of the Month 11 visit in RT001-006, PK samples will be obtained 30 minutes to 1 hour before the morning dose (pre-breakfast); and 30 min, 1, 2, 4 (pre-lunch), 8 (pre-dinner), 12 (post-dinner) and 24 hours after the initial morning dose.

The second optional sub-study is a 6-month study to evaluate the washout blood levels of RT001 after treatment in RT001-006 is completed. Depending on the timing of entry into the sub-study, washout pharmacokinetic (PK) samples will be obtained at 7 days, 4, 12, and 24 weeks after the last dose to determine the trough concentration of deuterated linoleic acid (D2-LA), deuterated arachidonic acid (D2-ARA), nondeuterated linoleic acid (H2-LA) and nondeuterated arachidonic acid (H2-ARA) in plasma, and D2-LA, D2-ARA H2-LA, and H2-ARA in red blood cells.

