8. INVESTIGATIONAL PLAN

8.1. Study Design

This is a randomized, double-blind, placebo-controlled study to evaluate the efficacy, safety, and tolerability in subjects with FRDA following the oral administration of study drug (active or placebo capsules).

Subjects will self-administer the study drug orally with meals. While on study drug, subjects are recommended to avoid eating foods high in PUFAs. Subjects will keep food journals from screening through the completion of month 1 on study drug. After month 1, subjects will keep 2-week food journals prior to next scheduled onsite visit. Subjects (or parents/caregivers, as applicable) will have an initial call and as needed with the diet coach to discuss food journal completion requirements.

A total 60 FRDA subjects will be enrolled. Subjects will be randomized to active [9 capsules of RT001 (8.64 g/day) for the first month, followed by 6 capsules of RT001 (5.76 g/day)] or placebo in a 1:1 ratio. Randomization will be stratified by FARS Neurological score: ≤45 and >45. Enrollment of patients with age > 25 will be capped at 25 % of the total enrollment.

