Subjects will self-administer orally 9 capsules daily for the first month with a meal: 3 capsules with breakfast, 3 capsules with lunch, and 3 capsules with dinner for the first month. After this initial period the dose will be reduced to 6 capsules daily with a meal: 3 capsules with breakfast, and 3 capsules with dinner for the remainder of the trial, while on study drug. If a subject is unable to tolerate study drug because of adverse events during the initial loading period, the dose may be reduced to six capsules daily (5.76 g total dose) given as 3 capsules with breakfast, and 3 capsules with dinner. If a subject is unable to tolerate study drug because of adverse events after the dose reduction to six capsules daily (5.76 g total dose), the dose may be spread over three meals (2 capsules at breakfast, 2 capsules with lunch, and 2 capsules with dinner). If the subject is still unable to tolerate study drug after spreading it over three meals, the total dose may be reduced by 1-2 capsules/day, preferably by reducing the dose for a meal from 2 to 1 capsule(s) as needed. After 2 weeks of taking a dose of less than 6 caps/day, the subject should try to increase the dose to 6 capsules/day given as 2 capsules TID given with meals. If 6 caps/day is not tolerable, the subject can take the drug at the dose of less than 6 caps/day that was tolerable. The last dose of study drug will be taken at 4 weeks from Day 330 visit.

Participation is anticipated to require 13 months.

- Screening: Up to 30 days from start of treatment
- Treatment Period: treatment for a 12-month period

Safety assessments include physical and neurologic examinations, vital signs, 12-lead electrocardiogram (ECG) tracing, and clinical laboratory tests (hematology, clinical chemistry,

lipid profile, coagulation, and urinalysis) to identify adverse events (AEs). Adverse events will be evaluated for incidence, severity, and relationship to study drug.

The first dose of the study drug will be taken on Day 1. Bioanalytical measurements will be performed to determine the concentration of D2-LA, deuterated arachidonic acid (D2-ARA), nondeuterated linoleic acid (H2-LA) and nondeuterated arachidonic acid (H2-ARA) in plasma and red blood cells. Blood samples will be collected at month 4 (Day 120 ± 30 days), at month 8 (Day 240 ± 30 days), and at month 11 (Day 330 ± 30 days). All samples are to be obtained prior to dosing and prior to breakfast.

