12.2. Exercise Testing Using CPET

Subjects will perform exercise testing using the CPET protocol at Screening, on Day 1, Day 120 (\pm 30 days), Day 240 (\pm 30 days), and Day 330 (\pm 30 days). Peak work rate and VO₂ MAX will be measured during incremental exercise testing on a recumbent bike. All tests should be done at approximately the same time for each visit. CPET should occur after fasting (if the subject has had a meal/snack) for a minimum of 2 hours, with neither caffeine nor nicotine for at least 12 hours before testing. Fluid consumption during the fasting period is limited to water, preferably at room temperature. Physical activity during the 24 hours prior to testing should be minimized. Routines followed for the initial laboratory assessments with respect to diet and physical activity should be duplicated for each subsequent visit. Subjects may take as much resting time as they

need between the bike test and the T1MW/T25FW. Detailed testing instructions will be provided in a separate manual.

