13.9. Optional PK Profile Sub-Study

The following procedures will be performed on Day 1:

- A blood sample for PK will be obtained at hour -1.0 to -0.5 (pre-breakfast, pre-dose),
- Subjects will take the morning dose of study drug at the clinic with their breakfast,
- A blood sample for PK will be obtained hour $0.5 (\pm 5 \text{ min})$,
- A blood sample for PK will be obtained hour 1 (\pm 5 min),
- A blood sample for PK will be obtained hour 2 (\pm 10 min),
- A blood sample for PK will be obtained hour $4 (\pm 15 \text{ min})$ (pre-lunch),
- A blood sample for PK will be obtained hour 8 (\pm 15 min) (pre-dinner),
- A blood sample for PK will be obtained hour $12 (\pm 60 \text{ min})$ (post-dinner)

The following procedures will be performed on Day 2:

• A blood sample for PK will be obtained on Hour 24 (pre-dose, pre-breakfast)

Dosing:

- The subject will only take the morning dose on the PK collection day. They will skip the evening dose.
- The subject should resume regular dosing schedule after morning PK draw on Day 2.

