19.12.2. Study Design

At selected sites, subjects who are enrolled in RT001-006 will be invited to participate in this study. At the time of the Month 11 visit in RT001-006, PK samples will be obtained 30 minutes to 1 hour before the morning dose; and 30 min, 1, 2, 4, 8, 12 and 24 hours after the initial morning dose. It is recommended that the blood draws are done on a different day than the study procedures for the Month 11 visit in RT001-006.

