19.12.6. Sample Size

Subjects who are enrolled in RT001-006 will be invited to participate in this study. Because the study treatment (active or placebo) in RT001-006 is blinded, a minimum of 10 subjects will be enrolled to ensure that at least 5 subjects who are randomized to active are enrolled in this study. An unblinded person may be asked to verify that at least 5 of the selected subjects were randomized to active. Additional subjects may be added as needed.

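### The optional PK profile, which omits an evening dose, may be run immediately before the Day 330 visit, so the Month 11 trough and the primary CPET may depart from the usual routine in some sub-study participants

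*Combined protocol and SAP*

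**What the plan says.** **Timing of the profile.** Section 12.8.1 states: "The first is a 24hr PK Profile at steady state that will occur immediately before or after the Day 330 visit". The synopsis (PK/Biomarker Analysis) and Section 8.1 leave the same choice open. Section 12.8.1 goes on to place the samples at the time of the Month 11 visit, and so does Section 19.12.2. The only separation is advisory (Section 19.12.2): "It is recommended that the blood draws are done on a different day than the study procedures for the Month 11 visit". Neither an order nor a minimum interval is fixed.

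**The profile day.** Section 13.9: "The subject will only take the morning dose on the PK collection day. They will skip the evening dose". Dosing restarts only after the 24 h sample: "The subject should resume regular dosing schedule after morning PK draw on Day 2". Sections 9.1.1, 19.12.7 and 19.12.8 add a standardised clinic breakfast, eight timed draws and an overnight stay near the site.

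**The Day 330 visit.** Section 13.8 schedules the main-study PK and biomarker samples before the morning meal, then the morning CPET. That CPET supplies the primary MVO2 endpoint (Section 7.1). Section 12.2 asks for constant preparation: "Routines followed for the initial laboratory assessments with respect to diet and physical activity should be duplicated for each subsequent visit".

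**Size and remaining dosing.** Section 19.12.6 says that "a minimum of 10 subjects will be enrolled to ensure that at least 5 subjects who are randomized to active" are included. Section 8.1 gives the trial size, "A total 60 FRDA subjects will be enrolled", and the end of dosing: "The last dose of study drug will be taken at 4 weeks from Day 330 visit".

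**The concern.** The sub-study can spill over into the main study at its deciding visit, and does so in different ways depending on the order.

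- **Profile on the day before.** The Month 11 pre-dose sample falls on PK Day 2, before regular dosing has resumed. It is then not a trough of the breakfast-and-dinner regimen, yet Section 14.1 uses such samples to describe the lowest steady-state exposure. The CPET that morning follows a day of timed draws, a set breakfast and an overnight stay. No such day preceded the baseline, Day 120 or Day 240 tests, which runs against the aim of Section 12.2.
- **Profile on the same day.** The pre-dose sample stays on schedule, but the CPET has to fit around the profile's meals and draws.

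At stake are the Month 11 exposure summary for active participants and the comparability of each participant's final CPET with his or her own baseline. Neither problem is needed to obtain the profile.

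**Working it through.** **1. How many subjects.** Ten is the minimum for the whole sub-study, with profiles before and after the visit combined. No section says how many are to be done before. If a share q of 10 profiles comes first, the number exposed is 10q:

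| q | Subjects | Expected on active | Share of 60 |
|---|---|---|---|
| 0 | 0 | 0 | 0% |
| 0.25 | 2.5 | 1.25 | 4.2% |
| 0.5 | 5 | 2.5 | 8.3% |
| 0.75 | 7.5 | 3.75 | 12.5% |
| 1 | 10 | 5 | 16.7% |

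With 30 of 60 subjects on active, 10 volunteers drawn without regard to arm include 5 active on average (95% range 2 to 8, hypergeometric).

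**2. Change in the trough.** Inputs are the mean terminal half-lives of plasma D2-LA in Section 6.4 and Table 7: 42.3 h (Cohort 1, n = 5) and 30.3 h (Cohort 2, n = 4). The usual dinner-to-breakfast gap is assumed to be 12 h. After the profile it is 24 h. With mono-exponential decline, the ratio of the 24 h value to the 12 h value is 2^(−12/t½):

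- t½ = 30.3 h: 2^(−12/30.3) = 0.760, which is 24.0% lower.
- t½ = 42.3 h: 2^(−12/42.3) = 0.821, which is 17.9% lower.

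Cross-check from the Cohort 2 concentrations in Table 7: 359.9 µg/mL at about 6 h falls to 86.2 µg/mL at 72 h. The half-life is 66 × ln 2 / ln(359.9/86.2) ≈ 32 h, which agrees with the tabulated mean. The spread is wide, however. One SD (18.3 h) either side of the Cohort 2 mean gives half-lives of 12.0 and 48.6 h, and reductions of 50% and 16%.

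**3. The same-day case.** Breakfast starts at Hour −0.5 and is to be finished within 30 minutes, and lunch follows the 4 h draw (Section 19.12.8). CPET must be in the morning after at least 2 h of fasting (Section 13.8). If CPET follows that breakfast, it has to fit between the 2 h and 4 h draws.

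**4. An outer bound on power, for illustration only.** Section 14.2 claims over 99% power for 30 versus 30, difference 15.8, SD 11.1 and two-sided alpha 0.05. The noncentral t calculation gives 99.97%, so the figure reproduces. If 5 of 30 active subjects lost the entire effect, the difference would be 15.8 × (1 − 5/30) = 13.17 and power 99.5%. With a smaller assumed standardised effect of 0.74 (about 80% power), the same total loss gives 65%, and a loss of one quarter of the effect in those 5 gives 77%. Section 14.2 is labelled as peak workload, not MVO2. Nothing in the documents suggests that one skipped dose removes any part of the effect, so these figures only show what extreme assumptions would do.

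**The case against.** The case for leaving the text alone has real weight.

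- **Consent.** The synopsis (Study Design) allows consent at the Day 330 visit or at the first draw. Those who consent at the visit cannot already have had the profile. This makes running it first less likely, but does not rule it out.
- **Placebo.** About half of participants take safflower oil, and a skipped capsule does not alter their D2-LA. This stands for the trough. The change in CPET preparation applies to both arms.
- **Recorded times.** Section 12.8.1 requires the time of the last dose to be recorded and actual sampling times to be used, so a 24 h gap is visible. This also stands. What is missing from the protocol is a rule for excluding or adjusting such a sample. The PK summary is descriptive and does not enter the primary model.
- **Ordinary visit burden.** All subjects agree to stay locally, visits may spread over several days, and blood is drawn at every visit. Section 12.2 still applies to participants and asks for little activity in the preceding 24 h, which a day of draws need not breach. It is therefore too strong to say that the rule is broken. Its aim is made harder to meet.
- **Unseen documents.** The CPET manual, the laboratory manual and the separate PK analysis plan may settle order or handling. They cannot be checked here, and the protocol text that sites follow is permissive.

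**Conclusion.** The protocol permits a profile with an omitted evening dose immediately before the Day 330 visit, or on the same day. In the first case the Month 11 pre-dose sample may be taken about 24 h after the last dose. Plasma D2-LA in an active participant would then be roughly 18% to 24% lower. That range assumes mono-exponential decline, a usual 12 h gap, and mean half-lives from a small 28-day study at other doses. In either case the final CPET may be done under preparation that differs from the subject's earlier tests.

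Two stronger readings are tempting and are not supported. A reader might infer from the sub-study minimum that at least 10 of 60 subjects will have their Month 11 trough and primary CPET off regimen. Ten is the size of the whole sub-study, so the supported range is from none to all of the 10 or more participants, about half of them on active. A reader might also infer that the primary result is biased. No section links one skipped dose after 11 months to MVO2. An effect is possible, but it is neither shown nor sizeable from the documents.

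This is a minor point and a cheap improvement.

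**What to change.** Reconcile the synopsis (PK/Biomarker Analysis) and Sections 8.1, 12.8.1 and 19.12.2, which variously place the profile before, after or at the time of the visit. State that it starts on a later day, once all Day 330 assessments (Month 11 PK and biomarker samples, CPET and T1MW) are complete, and while the subject is still within the remaining 4-week dosing period. Make the separate day mandatory rather than recommended. With every profile after the visit, the number exposed is zero.

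This fits the existing plan. Section 15.8 already expects the profile to start and stop within the dosing window, and consent can be taken at the Day 330 visit. The change concerns only the order of assessments, not the dosing regimen. It needs about one sentence in an amendment, repeated where the timing is stated, and no extra draws or subjects. The cost is less scheduling choice for sites, and possibly a longer stay or a return trip for travelling subjects.
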